1.3. GLOSSARY OF ABBREVIATION

AE Adverse event

AESI Adverse event of special interest

AIMS Abnormal involuntary movement scale

ALT Alanine aminotransferase

ANOVA Analysis of variance

AST Aspartate aminotransferase
ATC Anatomical Therapeutic Class

AUC Area under the plasma concentration-time curve (ng.h/mL)

AUC₀₋₂₄ Area under the plasma concentration-time curve from time 0 to

concentration C24 at the 24-hour time point (ng.h/mL)

 AUC_{∞} Area under the plasma concentration-time curve from time zero to infinity

(ng.h/mL)

BARS Barnes akathisia rating scale
BFB-520 Metabolite of roluperidone
BLQ Below limit of quantitation

BMI Body mass index
BUN Blood urea nitrogen

CGI-S Clinical global impression - severity rating

CI Confidence interval

C_{last} Last measurable concentration (ng/mL)
C_{max} Maximum drug concentration (ng/mL)

CSR Clinical study report

C-SSRS Columbia suicide severity rating scale

CV Coefficient of variation

CYP2D6 Cytochrome P450 2D6 enzyme

ECG Electrocardiogram

eCRF Electronic case report form

EOS End-of-study

LLN Lower limit of normal laboratory reference range

MedDRA Medical dictionary for regulatory activities

Minerva Neurosciences, Inc.

MIN-101C18

Statistical Analysis Plan Final Version

NA Not applicable

NM Normal metabolizer

PCS Potentially clinically significant

PD Pharmacodynamic
PK Pharmacokinetic
PT Preferred term

QTc QT interval value corrected for heart rate

QTcB QT interval value corrected for heart rate using Bazett's formula
QTcF QT interval value corrected for heart rate using Fridericia's formula

SAE Serious adverse event

SAF Safety set

SARS-CoV Severe acute respiratory syndrome coronavirus 2

SCR Screening

SD Standard Deviation

SEM Standard Error of Mean

SI Le Système International d'Unités (International System of Units)

SOC System Organ Classification

TEAE Treatment-emergent adverse event

 $t_{1/2}$ Terminal elimination half-life

T_{max} Time to maximum drug concentration (h)

UNL Upper normal limit of laboratory reference range

WHO World Health Organization

Final Version

2. OBJECTIVES

Primary Objective:

To evaluate the pharmacodynamics (PD), including safety and tolerability of the coadministration of roluperidone 64 mg and olanzapine.

- Adverse events (AEs)
- Laboratory evaluations
- Physical examination (including weight, baseline height and BMI)
- Vital signs (including blood pressure, heart rate, respiratory rate, pulse, temperature)
- 12-Lead electrocardiograms (ECGs)
- Extrapyramidal symptoms (assessed by Abnormal Involuntary Movement Scale (AIMS) and Barnes Akathisia Rating Scale (BARS))
- Suicidal ideation (assessed by the Columbia Suicide Severity Rating Scale (C-SSRS))

Secondary Objective:

To evaluate the effect of the coadministration of roluperidone and olanzapine on the pharmacokinetics (PK) of roluperidone in subjects with moderate to severe negative symptoms of schizophrenia. The secondary endpoint, PK, will include the following parameters:

- PK parameters of roluperidone and its metabolite, BFB-520, following single dose and at steady state.
- PK parameters of roluperidone and BFB-520 when administered concomitantly with olanzapine.
- PK parameters of olanzapine administered concomitantly with roluperidone compared to its pharmacokinetic profile based on monotherapy administration from published literature.

PK parameters are included but are not limited to the variables given below:

- C_{max}: observed maximum plasma concentration (ng/mL).
- t_{max} : time to reach the observed maximum plasma concentration (h).
- AUC₀₋₂₄: area under the plasma concentration-time curve from time 0 to concentration C₂₄ (ng.h/mL) at the 24-hour time point.
- AUC_{∞} : area under the plasma concentration-time curve from time 0 to infinite time, calculated according to the following equation $AUC_{\infty} = AUC_{last} + C_{last} / \lambda z$ (ng.h/mL), where C_{last} is the last measurable plasma concentration and λz is the terminal elimination rate constant.

3. GENERAL STATISTICAL CONSIDERATIONS

3.1. SAMPLE SIZE AND POWER

The planned sample size is approximately 18 subjects dosed with 64 mg roluperidone in Treatment Phase 1 such that at least 12 subjects can complete dosing with 64 mg roluperidone and 10 mg olanzapine during Treatment Phase 2. The selected sample size is sufficient to calculate the 90% confidence interval of the estimated ratio of C_{max} and AUC of roluperidone with and without coadministration of olanzapine for a true within subject standard deviation of 0.25 or 0.40 with maximum imprecision of 20.5% or 30.8%, respectively.

3.2. RANDOMIZATION AND BLINDING

This is an open-label, one-sequence study; therefore, randomization and blinding will not be performed. Eighteen (18) subjects will be enrolled in the study to ensure 12 subjects complete the study. Eligible subjects will be assigned a subject identification number in sequential order.

3.2.1. Examination of Subject Subsets

Select PK summaries will be presented by sex, as detailed in Section 5.2.4.

3.2.2. Multiple Testing and Comparisons

All analyses will be conducted without adjustments for multiple comparisons.

3.2.3. Missing Data and Outliers

Every effort will be made to obtain required data at each scheduled evaluation from all subjects who have been treated. For analysis purposes, imputation of dates may be necessary and is described below in Section 3.2.3.1. Additionally, some results may be reported as alphanumeric. For the purposes of calculating summary statistics, these values may be imputed as described in Section 3.2.3.2. No other imputation of values for missing data will be performed for this study.

3.2.3.1. Missing Dates

An incomplete date is any date for which either the day, month or year is unknown, but all three fields are not unknown. An incomplete date occurs when the exact date an event occurred or ended cannot be obtained from a subject.

For many of the analyses, a complete date is necessary in order to determine if the event should be included in the analysis (i.e., if the event is treatment-emergent) or to establish the duration of an event. In such cases, incomplete dates will be imputed.

For the purposes of handling partially reported start and stop dates for an event the following algorithm will be applied:

• Missing start day, but month and year present:

If the event occurs in the same month and year as the dosing of the study drug, then the start day of the study drug will be assigned to the day of first dose of the study drug.

Otherwise, the start day will be set to the first day of the month.

• Missing start day and month, but year present:

If event occurs in the same year as the study drug dosing, then the start date of the event will be assigned to Day 1 of Treatment Phase 1.

Otherwise, the start day and month will be set to 01 January.

• Missing all components of a start date:

Assign the date of Day 1 of Treatment Phase 1.

• Missing end day, but month and year present:

The day will be set to the last day of the month.

• Missing end day and month, but year present:

The end day and month will be set to the date of study completion (EOS Visit Date).

However, if the study completion year is greater than the year of the event, then the day and month will be set to 31 December.

• In the event of a completely missing end date (year not present and ongoing not checked), the end date will be imputed as the date of study completion or discontinuation. If the imputed date is later than the date of study withdrawal, then the date of study withdrawal will be imputed for the date.

If any imputed date causes the end date to occur prior to the start date of the event, the start date of the event will be used for the imputation of the end date. If any imputed date causes the start date of the event to occur after the end date of the event, the end date of the event will be used for the imputation of the start date. In subject data listings, start and stop date of events will be displayed as reported on the eCRF (i.e., imputed values will not be listed).

3.2.3.2. Imputation of Alphanumeric Data

Should there be instances where a clinical laboratory parameter is reported with imbedded non-numeric characters, as for example, "<0.1" or ">10", the data will be imputed for the purpose of quantitative summaries. The actual values as reported in the database will be presented in data listings.

For incorporation in quantitative summaries, the following imputation rules will be employed:

The limit of quantitation will be increased by one level of precision in the direction of the symbol that precedes the value. For example, "<0.1" will be imputed to "0.09", while ">0.1" will be imputed to "0.11", and ">10" will be imputed to "10.1". Values reported as "\leq" or "\geq" will be imputed

Final Version

similarly. For example, "\(\leq 0.1\)" will be imputed to "0.09". For PK values, values reported as "BLQ" will be imputed to 0. BLQ values will not be presented on graphs for plots of semi-log values.

3.2.4. Presentations by Time Point

Subjects are institutionalized from washout phase to Day 19 (+2 days after the last dose on Day 17). See Section 1.2 for specifics regarding when assessments are measured within a phase. The timeline of assessment measurements is repeated for each treatment phase. Assessments after screening and occurring on Day -1 after a washout period will be attributed to the following treatment phase.

Nominal Time Points as obtained from the eCRF or laboratory will be utilized for summary displays. Unscheduled visits will not be windowed and be excluded from summary tables and figures but will be listed.

If assessments are collected multiple times within a given nominal time point, the result closest to the scheduled time will be used for summary presentations. If two measurements have the same distance to the expected time, the earlier value will be used. If a scheduled assessment and an early termination assessment are collected within a given time point window, the value from the scheduled assessment will be chosen over the value from the early termination assessment.

3.2.5. Definitions and Terminology

Baseline Value

For quantitative safety measures, Baseline will be defined as the last valid evaluation completed before the study drug administration on Day 1. For ECG measures, including QTcF, Baseline will be defined as the mean of the triplicate set (total of 3 ECGs) performed pre-dose on Day 1 in Treatment Phase 1. This will also be referred to as Study Baseline.

A second Baseline will be used and will be referred to as the Treatment Phase 2 Baseline. For ECG, Treatment Phase 2 Baseline will be the mean of the triplicate ECGs (total of 3 ECGs) performed predose on Day 8.

Study Day

Study Day is defined relative to Day 1. Thus, the study day of an event occurring on or after Day 1 is calculated as:

Study Day = event date - date of Day 1 + 1.

The study day of an event occurring prior to Day 1 is calculated as:

Study Day = event date - date of Day 1.

Days on Study

Days on Study is calculated as Final Day on Study based on the EOS eCRF page – First Day on Study Drug + 1.

Treatment Phase Day

The study day within a treatment phase. Treatment Phase Day will be defined within each Treatment Phase 1 or 2.

Final Version

Treatment Phase Day = event date - date of Day 1 of Treatment Phase X + 1.

Study Time Point

Study Time Point is the nominal time point as recorded on the CRF.

Change from Baseline

Change from Baseline for a given endpoint is defined as the Study Time Point X value minus the Baseline Value. Change from Baseline may be study-specific (i.e., across all study phases), or Treatment Phase-specific (within any specific Treatment Phase). In the latter case, Baseline will be Treatment Phase specific.

Adverse Event

An adverse event is any untoward medical occurrence in a clinical study subject administered a medicinal (investigational or non-investigational) product. An adverse event does not necessarily have a causal relationship with the treatment. An adverse event can, therefore, be any unfavorable and unintended sign (including an abnormal finding), symptom, or disease temporally associated with the use of a medicinal (investigational or non-investigational) product, whether or not related to that medicinal (investigational or non-investigational) product.

This includes any occurrence that is new in onset or aggravated in severity or frequency from the Baseline condition, or abnormal results of diagnostic procedures, including laboratory test abnormalities.

All adverse events will be recorded on the Adverse Event page of the CRF.

Serious Adverse Event (SAE)

An SAE is defined as any AE that results in any of the following:

- **Death**: The subject died as the result of the event.
- **Life-threatening event**: Any AE that places the subject, in the view of the Investigator or Sponsor, at immediate risk of death from the AE as it occurred, i.e., does not include an AE that had it occurred in a more severe form, might have caused death.
- Required or prolonged inpatient hospitalization: The AE resulted in hospitalization or prolonged an existing hospitalization. Since hospitalization may be part of the study, only hospitalizations that are longer than expected based on Investigator judgment, will be considered prolonged hospitalizations.

Final Version

- **Persistent or significant disability/incapacity**: An AE that results in a substantial disruption of a person's ability to conduct normal life functions.
- Congenital anomaly/birth defect: A congenital anomaly/birth defect that occurs in the offspring of a subject exposed to the Investigational Product.
- Important medical events: An AE that may not result in death, be life-threatening, or require hospitalization may be considered an SAE when, based upon appropriate medical judgment, the event may jeopardize the subject and may require medical or surgical intervention to prevent one of the outcomes listed above.

Treatment-emergent Adverse Event (TEAE)

Any recorded Adverse Event that occurs on or after the initiation of study drug is considered treatment-emergent. TEAEs will be attributed to the most recent treatment group that was received prior to the start of the AE. For AEs with partial dates, the event will be attributed to the earliest period the event could have occurred in based on the date. AEs that occur on a Day 1 of any Treatment Phase with no time will be attributed to the treatment received on that day.

Adverse Event of Special Interest (AESI)

AESIs are defined as the any of the following events:

- Syncope
- Sudden death, cardiac death
- TdP, QT/QTc prolongation, long QT syndrome
- ECG T wave and U wave abnormalities
- Ventricular arrhythmia, tachycardia, fibrillation / flutter

Treatment-emergent Clinically Significant Laboratory Abnormality

A Treatment-emergent Clinically Significant Laboratory Abnormality is defined as any post-Baseline laboratory assessment occurring from Day 1 to the EOS determined to be clinically significant by the investigator, and for which the Baseline is not considered clinically significant. If the Baseline value is missing, normal, or not clinically significant, any clinically significant abnormality that occurs following initiation of study drug is considered treatment-emergent.

Concomitant Medications

Concomitant medications are those medications taken on or after the initiation of roluperidone on Day 1 of Treatment Phase 1. This definition includes medications that started prior to the initiation of roluperidone and continued concomitantly with roluperidone.

Prior Medications

Prior medications are those medications taken and stopped prior to the initiation of roluperidone.

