Minerva Neurosciences, Inc. Protocol MIN-101C18

Confidential

Period	SCR	Admis- sion	BL		T	reatn	nent	Phas	e 1			Treatment Phase 2						EOS/ ET					
Study Day	-28 to -3	-2	-1	1	2	3	4	5	6	7	8	9	10	11	12	13	14	15	16	17	18	19	31 (+2)
Adverse events	X	←•	• • •	• • •	• •	• • •	• • •	• • •	• • •	• •	• • •	• • •	• • •	• • •	• • •	• • •	• • •	• • •	• • •	• • •	• • •	• • • •	$\cdots \rightarrow$

NOTE: There is no washout period between Treatment Phases.

Abbreviations: AIMS = abnormal Involuntary Movement Scale; BARS = Barnes Akathisia Rating Scale; BL = baseline; CGI-S = Clinical Global Impression – Severity C-SSRS = Columbia Suicide Severity Rating Scale; ECG = electrocardiogram; EOS = end-of-study; ET = early termination; PK = pharmacokinetics; SCR = screening; SCR = screening.

^a Verify eligibility.

^b Vital signs include blood pressure (standing and supine), pulse, oral/tympanic temperature, and respiratory rate. During Treatment Phase 1, vital signs are assessed prior to PK sampling at pre-dose and 6 hours post-dose on Days 1-7. During Treatment Phase 2, vital signs are assessed prior to PK sampling at pre-dose and 6 hours post-dose on Days 8-17 and 24 hours and 48 hours after last dose of study drug is administered (eg. Days 18 and 19).

^c Three sets of triplicate ECGs (1 minute apart within 5 minutes; total of 9 ECGs are recorded at Baseline (Day -1). Other ECG assessments are recorded in triplicate prior to PK sampling. During Treatment Period 1, ECGs are recorded at pre-dose and 6 hours post-dose on Days 1-7. During Treatment Phase 2, ECGs are recorded pre-dose and 6 hours post-dose on Days 8-17 and 24 hours after last dose of study drug is administered (eg, Days 18 and 19).

^d CYP2D6 genotyping to be performed.

e Urinalysis will be performed by dipstick. Urine will be sent to the laboratory for microscopic analysis only in the event that the dipstick results are abnormal.

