6.1.3. Baseline Visit

At the Baseline visit on Day -1, subjects will complete admission procedures and confirm eligibility for enrollment. Vital signs, electrocardiogram (3 sets of triplicate ECG), body weight, and height will be measured. Laboratory samples for hematology, clinical chemistry, and urinalysis (by dipstick) will be performed for all subjects. AIMS, CGI-S, BARS, and C-SSRS will also be administered.

6.1.4. Treatment Phase 1

In Treatment Phase 1, beginning on Day 1, subjects will receive 64 mg roluperidone each day at approximately the same time (between approximately 7:00 and 10:00 AM), followed by sequential collection of blood samples for measurement of plasma concentrations of roluperidone and ECG assessments, until Day 7. On Days 1 and 7, subjects will receive the study drug after fasting for at least 9 hours starting the night before. Subjects will receive standardized light meals approximately 2 hours after dosing. Vital signs, ECGs (in triplicate), and PK samples at specified time points will be collected throughout Treatment Phase 1. AIMS, CGI-S, BARS, C-SSRS will be administered on Day 7. Subjects will remain at the clinic after Day 7 to continue Treatment Phase 2.

6.1.5. Treatment Phase 2

In Treatment Phase 2, beginning on Day 8 subjects will receive study drugs (roluperidone and olanzapine) each day at approximately the same time followed by sequential collection of blood samples for measurement of plasma concentrations of both drugs and ECG assessments until Day 17. On Day 17, subjects will receive the study drug after fasting for at least 9 hours starting the night before. Subjects will receive standardized light meals approximately 2 hours after dosing. Vital signs, ECGs (in triplicate), and PK samples at specified time points will be collected throughout Treatment Phase 2. AIMS, BARS, and will be administered on Day 8, and AIMS, CGI-S, BARS, CC-SSRS will be administered on Day 17. Subjects may be released from the clinic after the collection of the last plasma sample (at least 48 hours after the last administration of the study drugs); however the inpatient period may be extended at the discretion of the investigator.

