7.2. Stopping Criteria

Subjects who meet any of the following stopping criteria will be discontinued from the study:

- 2. CGI-S worsening of more than 2 points.
- 3. Suicidal ideations or behavior.
- 4. Occurrence of an AE, which could jeopardize the subject's health as per investigator opinion.
- 5. Worsening of psychotic symptoms or occurrence of any dangerous behavior against self or others as per investigator opinion.
- 6. Significant increase in ALT (ie, $> 5 \times ULN$).
- 7. Abnormal laboratory results with simultaneous increases of total bilirubin ($> 2 \times ULN$), ALT or AST ($> 3 \times ULN$) with AP ($< 1.5 \times ULN$).
- 8. Sustained mean QTcF value > 500 msec (confirmed by a second ECG under strict resting position and at minimum at 30-minute duration from the first measurement). The subject's treatment must be discontinued until mean QTcF values are obtained from the ECG central reader. If values are confirmed, the subject must be discontinued from the study; if not, the study treatment may be restarted at the discretion of the investigator.
- 9. Sustained mean increase of > 60 msec in the QTcF compared to Baseline (confirmed by a second ECG under strict resting position and at minimum at 30-minute duration from the first measurement). The subject's treatment must be discontinued until mean QTcF values are obtained from the ECG central reader. If values are confirmed, the subject must be discontinued from the study; if not, the study treatment may be restarted at the discretion of the investigator.

- 10. The subject requires treatment with another therapeutic agent that had been demonstrated to increase the QT interval or inhibit CYP2D6. In this case, discontinuation from the study should occur prior to the introduction of the new agent.
- 11. The subject experiences a syncope or severe dizziness not explained by other known causes, eg, documented orthostatic hypotension, Ménière disease.
- 12. The subject has an overt seizure or reports seizure-like activity (loss of consciousness, uncontrollable tremor not due to extrapyramidal symptoms).

The study will be stopped if 4 or more subjects are discontinued due to any of the criteria, except stopping criterion 4 if the AE is considered to be definitely not related to study drug and stopping criteron 10.

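### The SAP's QTcF Study Baseline is one Day 1 triplicate; it omits the nine ECGs from the protocol's Day -1 Baseline visit without giving a reason

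*SAP*

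**What the plan says.** Footnote c of the protocol's Time and Events Schedule reads: "Three sets of triplicate ECGs (1 minute apart within 5 minutes; total of 9 ECGs are recorded at Baseline (Day -1"). Protocol 6.1.3 places the Baseline visit on Day -1 and lists "electrocardiogram (3 sets of triplicate ECG") among its procedures. Every other ECG time point has one triplicate. SAP 1.2 repeats the nine-ECG footnote with the same Baseline label.

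SAP 3.2.5 then sets the ECG baseline, including QTcF, differently: "Baseline will be defined as the mean of the triplicate set (total of 3 ECGs) performed pre-dose on Day 1 in Treatment Phase 1". It calls this the Study Baseline. A second baseline serves the combination phase: "Treatment Phase 2 Baseline will be the mean of the triplicate ECGs (total of 3 ECGs) performed predose on Day 8".

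SAP 5.3.4 reports ECG changes from both baselines. It counts subjects with QTcF increases of >30-60 msec and >60 msec, each subject once in the worst category reached. Protocol 7.2, criterion 9, discontinues a subject for a "Sustained mean increase of > 60 msec in the QTcF compared to Baseline", subject to a confirmatory ECG and central over-read. SAP section 7 anticipates no departure from the planned analysis.

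**The concern.** The protocol puts three times the usual number of ECGs at one visit and calls that visit Baseline. The SAP carries the schedule over and then leaves those recordings out of every change score, without comment.

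Two things are at stake. The first is precision. The worst-case categories compare each subject's whole post-dose series with one baseline value, so any error in that value shifts all of the subject's changes the same way. Protocol 1.2 names QT prolongation as a risk of roluperidone, QT/QTc prolongation is an event of special interest, and ECG belongs to the primary objective in SAP section 2. About 18 subjects are planned, so one or two spurious entries would be noticeable.

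The second is consistency. If criterion 9 is applied against Day -1 while the tables use Day 1, a subject can be discontinued for >60 msec and be missing from the >60 msec row, or the reverse. Discontinuations under criterion 9 also count toward the four-subject rule for stopping the study.

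**Working it through.** **Counts from the documents.** Day -1: 3 sets × 3 = 9 ECGs, as footnote c states. SAP Study Baseline: 1 set × 3 = 3 ECGs. All pre-dose ECGs: 9 + 3 = 12.

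Scheduled post-baseline sets: Day 1 at 6 h (1) + Days 2-17 pre-dose and 6 h (16 × 2 = 32) + Days 18 and 19 (2) + end of study (1) = 36.

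**Assumptions.** The documents give no QTcF variance. Let T be the within-subject SD of a triplicate mean without drug effect, and f the share of T² that lies between days. I take T = 8 and 10 msec, f = 0, 0.5 and 0.75, and normal errors.

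**SD of a change to a day after Day 1** is T × √(1 + v), where v is the baseline variance divided by T²:

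- Day 1 triplicate: v = 1.
- Nine Day -1 ECGs: v = f + (1 − f)/3.
- All 12 ECGs (weights 3/4 on Day -1 and 1/4 on Day 1): v = (9/16 + 1/16)f + (1 − f)/4 = 0.625f + 0.25(1 − f).

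| f | Day 1 only | Day -1 only | All 12 | Reduction, all 12 vs Day 1 |
|---|---|---|---|---|
| 0 | 1.414T | 1.155T | 1.118T | 21% |
| 0.5 | 1.414T | 1.291T | 1.199T | 15% |
| 0.75 | 1.414T | 1.354T | 1.237T | 13% |

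**Chance that a subject is counted with an increase >30 msec when there is no drug effect** (largest of 36 changes; 400,000 simulated subjects per row):

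| T (msec) | f | Day 1 only | Day -1 only | All 12 |
|---|---|---|---|---|
| 8 | 0 | 7.2% | 1.9% | 1.4% |
| 8 | 0.5 | 6.8% | 4.3% | 2.5% |
| 8 | 0.75 | 6.4% | 5.3% | 3.0% |
| 10 | 0 | 21.3% | 12.2% | 10.5% |
| 10 | 0.5 | 20.3% | 17.0% | 13.4% |
| 10 | 0.75 | 19.3% | 17.9% | 13.9% |

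The chance of a false >60 msec count was at most about 0.04% in any row, whichever baseline was used.

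**Chance difference between the Day 1 and Day -1 baselines.** SD = T × √(1 + f + (1 − f)/3), which is 1.155T to 1.354T: 9.2-10.8 msec at T = 8 and 11.5-13.5 msec at T = 10. A subject whose real increase lies near 60 msec can therefore be above the limit on one baseline and below it on the other.

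**Where the Day 1 baseline can do better.** For the Day 1 6-hour change, a same-day baseline cancels the day effect. Its variance is 2(1 − f)T², against (1.125f + 1.25(1 − f))T² for the pooled baseline. At T = 8 and f = 0.5 the SDs are √64 = 8.0 and √76 = 8.7 msec. At f = 0.75 they are √32 = 5.7 and √74 = 8.6 msec. At f = 0 the pooled baseline is better: √80 = 8.9 against √128 = 11.3 msec.

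**The case against.** The SAP's choice is prespecified and coherent. It agrees with the general rule in SAP 3.2.5 (last valid value before the first dose) and mirrors the Day 8 baseline: one pre-dose triplicate at the start of each phase. Day 1 pre-dose is drug-free with respect to study treatment. Day -1 also has a drawback. Protocol 6.1.1 lets psychotropics be stopped as late as Day -2, and Attachment 1 lists many antipsychotics and antidepressants as QT-prolonging. A residual effect on Day -1 could raise that baseline and shrink the measured increase, and three quarters of a pooled baseline would come from that day. All of this stands. It is why the fix keeps a Day 1-only table.

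The gain also depends on an assumed variance and is largest when sets are independent. When most variation is between days, the nine Day -1 ECGs alone add little; averaging over two days then supplies most of the benefit. This stands too, but the pooled baseline gave the lowest false >30 msec rate in every row of the table.

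A reader might infer more than the documents support:

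- *That the Day 1 baseline is invalid.* It is not. It is unexplained, and less precise for later days.
- *That the Day -1 ECGs are discarded.* SAP 5.3.4 still lists all ECG assessments; they are left out of the change scores only.
- *That criterion 9 is defined on the nine-ECG mean.* Protocol 7.2 says only Baseline. Day -1 follows from the protocol's naming of visits, not from an explicit statement.
- *That baseline noise will produce false >60 msec results.* At these SDs it almost never does.

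Finally, the rule and the table could disagree even with a common baseline. Criterion 9 needs confirmation by a second ECG, while the table takes the worst value and SAP 3.2.4 keeps unscheduled assessments out of summaries.

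**Conclusion.** The point holds in a moderate form. The SAP leaves nine scheduled baseline ECGs out of every QTcF change score without giving a reason, and Baseline has one meaning in the protocol's visit naming and another in the SAP's tables.

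Pooling all pre-dose ECGs would cut the SD of changes to later days by about 13-21%. It would lower false >30 msec counts from about 7% to 1.4-3% at a set-mean SD of 8 msec, and from about 19-21% to 10-14% at 10 msec. These figures rest on the assumed SDs, no drug effect, 36 post-baseline sets and a between-day share of 0 to 75%. They do not extend to the >60 msec category, where noise alone is negligible and only subjects with a real increase near the limit are affected. The Day 1 6-hour change may be better served by the same-day baseline, and changes from the Treatment Phase 2 Baseline do not depend on this choice.

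The mismatch with criterion 9 is a well-supported inference, which is reason enough to reconcile the two documents.

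**What to change.** 1. In SAP 3.2.5, define the ECG Study Baseline as the mean of all scheduled pre-dose sets: the three Day -1 triplicates and the Day 1 pre-dose triplicate (12 ECGs). Use it for the change-from-Study-Baseline results in Tables 14.3.7.1 to 14.3.7.3. Leave the Treatment Phase 2 Baseline as it is.
2. Repeat the >30-60 and >60 msec table with the Day 1-only baseline as a sensitivity analysis, and give the reason: Day -1 is closer to the psychotropic washout.
3. Reconcile Protocol 7.2 criterion 9 with the SAP by stating which Baseline it refers to. This review does not say which it should be.
4. List every subject whose >60 msec classification differs between the two baselines.

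The cost is one changed SAP definition, one extra table, one listing and one protocol clarification. The ECGs are already scheduled and centrally over-read. The downside is that part of the main baseline lies a day nearer to prior medication; the sensitivity table is there to show whether that matters.
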